dose, which all patients will receive). The length of the first cycle is 5 weeks and subsequent cycles are 2 weeks in duration.

In the Dose Escalation Cohort, there will be up to three dose levels explored in a standard '3+3' dose escalation design. Three subjects will be accrued at the starting dose level. If no DLTs are seen at that level, three subjects will be enrolled at the next dose level. If one of three subjects has a DLT at any dose level, an additional three subjects will be enrolled at that dose level. If one of six subjects experience DLT, then escalation may continue. If two or more subjects have DLT at any dose level, then that dose level will be considered to have unacceptable toxicity, the next lower dose level will have additional subjects enrolled. Up to six subjects will be enrolled at the maximum tolerated dose (MTD) before proceeding to the expanded cohort.

The Dose Expansion cohort will enroll subjects at the MTD and follow the treatment scheme described above.

Number of Subjects

The Dose Escalation Cohort will enroll 6 to 18 subjects.

The Dose Expansion Cohort will enroll 6 subjects.

A total of 12 to 24 evaluable subjects will be accrued to assess the safety and tolerability of intraperitoneal talimogene laherparepvec.

Estimated Length of Study Participation

Estimated duration of subject enrollment is 5 months.

Subjects may continue to receive study treatment until they receive up to 4 doses after the initial seroconversion dose, experience unacceptable drug-related toxicity, or disease progression. For subjects that discontinue study treatment with no documented disease progression and no subsequent anti-cancer treatment, they will be followed every 12 weeks or as clinically indicated with tumor evaluations until disease progression or start of new anti-cancer therapy is documented. All subjects will be followed for survival for 1 year after completing treatment.

Study Drug Regimen

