9.0 STATISTICAL ANALYSIS

9.1 General Analysis Considerations

Up to 30 subjects will be enrolled and treated. The intent to treat population is defined as all subjects who receive treatment with talimogene laherparepvec at the MTD.

The per protocol population is defined as all subjects who:

- Undergo treatment with talimogene laherparepvec
- Fulfill all inclusion and exclusion criteria
- Are evaluable for the primary efficacy criterion, TTP

The safety population consists of all the subjects who receive talimogene laherparepvec for whom safety data is available. All safety analyses will be carried out on this population.

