9.1.2 Primary Endpoint

The primary objective of the study is to define the safety and toxicity profile of talimogene laherparepvec in patients with peritoneal surface dissemination from gastrointestinal, fallopian tube, ovarian, or primary peritoneal tumors. The MTD across three dose levels will be determined as described in Table 3.1. The safety analyses will be performed on the safety population, as defined above. Incidence of adverse events occurring in 10% or more of patients will be summarized by Grade, overall and by dose level.

Adverse events will be described using the NCI CTCAE 5.0 criteria. Frequency and severity of adverse events according to the NCI CTCAE v 5.0 body system and severity criteria will be described. In addition, frequency of Grade 3 or 4 adverse events will be described separately. Causality will also be noted.

Laboratory assessments will also be described according to the NCI CTCAE criteria, with separate descriptions for Grade 3 or 4 laboratory abnormalities. Clinically significant laboratory abnormalities will be described as well. Serious adverse events will be summarized, including a causality assessment.

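### The only adverse-event table planned by dose level has a 10% incidence cut, so on the natural pooled reading an event in 2 patients leaves the dose comparison once 21 or more are treated

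*Combined protocol and SAP*

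**What the plan says.** The primary objective is the toxicity profile. Section 9.1.2 gives its analysis: "Incidence of adverse events occurring in 10% or more of patients will be summarized by Grade, overall and by dose level". The section then describes AEs by CTCAE body system and severity, adds that "frequency of Grade 3 or 4 adverse events will be described separately", and covers causality, laboratory abnormalities and serious events. None of these further outputs has an incidence cut, and none is said to be split by dose level.

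On the analysis set, Section 9.1.2 states: "The safety analyses will be performed on the safety population, as defined above". Section 9.1 defines it: "The safety population consists of all the subjects who receive talimogene laherparepvec for whom safety data is available". That set pools all dose levels.

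On size, the synopsis plans between 6 and 18 patients for escalation and a further 6 for expansion, and gives the overall figure: "A total of 12 to 24 evaluable subjects will be accrued". Table 3.1 allows 3 to 6 evaluable subjects at each of three levels, plus 6 at the MTD. Section 9.1 gives a different ceiling: "Up to 30 subjects will be enrolled and treated".

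**The concern.** The three dose levels span a 100-fold range (4×10^6 to 4×10^8 PFU), and a dose-escalation trial is run to see what changes along that range. A cut applied to the pooled count removes events that are rare overall because they cluster at one level. The one planned table that compares doses would then omit the pattern it should show.

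The DLT review does not fully make up for this. Sections 3.2 and 10.5 base the escalation decision on the first 5 weeks. That window contains the common seroconversion dose and one cohort-level dose, on Day 22. The other three cohort-level doses fall on Day 1 of Cycles 2 to 4. Section 3.2.1 also keeps some Grade 3 events out of the DLT definition, such as fatigue of any duration and non-hematologic toxicity that resolves within 3 days. For such events the by-dose AE table is the only planned comparison across levels.

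**Working it through.** **Plan's own size.** Escalation plus expansion gives 6 + 6 = 12 and 18 + 6 = 24, which reproduces the synopsis range. The ceiling of 30 in Section 9.1 does not follow from these inputs.

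**Threshold count.** With a pooled denominator, an event is shown if at least ceil(0.10 × N) patients have it. This is 2 patients for N = 12 to 20 and 3 patients for N = 21 to 30. At the boundary, 2/20 = 10.0% is shown and 2/21 = 9.5% is not. At N = 30, 2/30 = 6.7% is not. A single event is below the cut at every planned size (1/12 = 8.3%).

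**Sizes that the rules in Section 3.2 can produce.** I assume 6 patients at the MTD before the 6 expansion patients, and that the safety population equals the evaluable count. Treated patients who are not evaluable for DLT would raise N further.

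| Path | Patients at levels 1, 2, 3 | N | Event | Pooled | Shown by dose? |
|---|---|---|---|---|---|
| Level 3 rejected after 6, MTD level 2 | 3, 12, 6 | 21 | 2 of 6 at level 3 (33.3%) | 9.5% | No |
| Same, level 1 expanded | 6, 12, 6 | 24 | 2 of 6 at level 3 (33.3%) | 8.3% | No |
| MTD level 3 | 3, 3, 12 | 18 | 2 of 12 at level 3 (16.7%) | 11.1% | Yes |
| MTD level 3, one lower level expanded | 6, 3, 12 or 3, 6, 12 | 21 | 2 of 12 at level 3 (16.7%) | 9.5% | No |
| MTD level 3, both lower levels expanded | 6, 6, 12 | 24 | 2 of 12 at level 3 (16.7%) | 8.3% | No |
| Level 2 rejected after 6, MTD level 1 | 12, 6, 0 | 18 | 2 of 6 at level 2 (33.3%) | 11.1% | Yes |
| Level 3 rejected after 3, MTD level 2 | 3, 12, 3 | 18 | 1 of 3 at level 3 (33.3%) | 5.6% | No |
| Level 2 rejected after 3, MTD level 1 | 12, 3, 0 | 15 | 1 of 3 at level 2 (33.3%) | 6.7% | No |

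**Chance of omission (illustration).** Assume a true rate of 1/3 in 6 patients at one level and 0 elsewhere. At N = 21 to 30 the event is seen but falls below the cut when 1 or 2 patients have it: 6(1/3)(2/3)^5 + 15(1/3)^2(2/3)^4 = 0.263 + 0.329 = 0.59. At N = 18 only the single-patient case is dropped, with probability 0.26.

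**Cut within each level instead.** One event then qualifies in any level of up to 10 patients (1/3 = 33.3%, 1/6 = 16.7%), so 2 of 6 is always shown. In an MTD group of 12, a single event (1/12 = 8.3%) would still be dropped.

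**The case against.** The strongest objection is that the pooled denominator is not written down. The sentence can be read as judging the 10% separately in each display, and then 2 of 6 and 1 of 3 both appear. This stands as a limit: pooling is the natural reading given the safety population, but it remains an inference. The ambiguity itself needs settling in a primary analysis.

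A reader might also infer several stronger things that the documents do not support.

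- *That a toxicity in 2 of 6 patients at the dose carried forward disappears.* An MTD level holds 9 to 12 patients after expansion. On the standard path, exactly 6 at level 3 with N of 21 or 24 arises only when that level was rejected. For an MTD level of 12 the figure is 2 of 12.
- *That the cut can hide a rate that Section 3.2 calls unacceptable.* That rule concerns DLTs, which are counted per level with no incidence cut (Sections 3.2 and 10.5). The MTD decision is untouched.
- *That the events are lost.* They remain in the overall frequency and severity description and, if serious, in the serious-event summary. Table 10.2.2 also requires a line listing and tabulation of all AEs for the supporting company. None of these is stated to be by dose level.
- *That the Grade 3 or 4 limit causes the omission.* It does not. Grade 5 events still fall under the severity description and the serious-event criteria, and a Grade 5 toxicity is a DLT. They are missing only from the separate severe-event summary.

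**Conclusion.** The point holds in a limited form. If the 10% is taken over the pooled safety population, an event in 2 patients leaves the by-dose table at N of 21 or more, which includes the planned maximum of 24. That covers 2 of 6 at a rejected level 3 and 2 of 12 at an MTD level. An event in 1 of 3 patients at a level is left out at N of 15 to 18. Two events are shown at N of 20 or fewer. If the cut is taken within each level, the 2-of-6, 2-of-12 and 1-of-3 cases are all shown.

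The consequence is incomplete reporting of the dose comparison, mainly for non-DLT and later-cycle toxicity. Data collection, escalation and MTD selection are unaffected. It still deserves correction because the table serves the primary objective and the trial is too small to need a threshold. The Grade 3 or 4 wording is a separate and smaller gap.

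**What to change.** In Section 9.1.2, tabulate all recorded AEs (Grades 2 to 5, as Section 10.1 requires on the case report form) by grade, overall and by dose level, with no incidence cut. This is better than moving the cut inside each level, which could still drop a single event in 12 patients at the MTD. It also makes the denominator question irrelevant for this table.

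Separately, change the severe-event summary to Grade 3 or higher and give it by dose level. Reconcile the 12 to 24 in the synopsis with the ceiling of 30 in Section 9.1, since N sets the denominators.

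The cost is a longer AE table in a trial of at most 24 to 30 patients. No new data are needed.

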9.1.3 Correlative Endpoints

Viral load will be measured by number of copies/mL; patients are expected to have undetectable viral load at baseline and increased viral loads on treatment. Cytokine levels will be measured in pm/mL. For both of these endpoints logarithmic transformations will be used to achieve normality. Immune cell markers will be measured as percentage of subset cell types. Ninety percent (90%) confidence interval (CI) estimates of mean changes in viral load, cytokine levels, and immune markers from baseline will be constructed in the intent-to-treat population (n=12 No preliminary data are available for these endpoints.

The proportion of patients who achieve at least a 2-log change in viral load or cytokine level will be estimated. With 12 patients studied in the intent-to-treat population the 90% upper confidence bound (1-sided) for change in viral load is at most 0.185. The proportion of patients exhibiting at least a 2-log change in cytokine levels (positive or negative) can be estimated to within at most +/- 0.237 with 90% confidence. The proportion of patients exhibiting a change of at least 0.15 in magnitude will be estimated similarly for immune markers.

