For subjects who discontinue study treatment with no documented disease progression and no subsequent anti-cancer treatment, they will be followed every 12 weeks or as clinically indicated with tumor evaluations consisting of restaging scan with RECIST 1.1 evaluation and blood tumor markers, until disease progression or start of new anti-cancer therapy is documented

Correlative Studies

The association between biomarker expression and clinical outcomes will be explored with the following blood and tumor tissue specimen collections and specified time points from all subjects:

- *Tumor Tissue.* If available, archived FFPE tumor samples will be obtained from all subjects at the end of the study, upon PI request.
- *Viral Load.* Blood and urine will be collected at baseline (prior to seroconversion dose on Cycle 1 Day 1), Cycle 1, Day 8, Cycle 1 Day 15, prior to treatment on Cycle 1 Day 22, Cycle 1 Day 29, prior to treatment Cycle 2 Day 1, prior to treatment on Cycle 3 Day 1, prior to treatment on Cycle 4 Day 1, at disease progression or off treatment, and 30-day off treatment follow-up. Peritoneal fluid will be collected at baseline (prior to seroconversion dose on Cycle 1 Day 1), prior to treatment Cycle 2 Day 1, prior to treatment on Cycle 4 Day 1, at disease progression or off treatment, and 30-day off treatment follow-up
- *Peritoneal Cytokine Levels.* Collected at baseline (prior to seroconversion dose on Cycle 1 Day 1), prior to treatment on Cycle 2 Day 1, prior to treatment on Cycle 4 Day 1, and at disease progression or off treatment, and 30-day off treatment follow-up.
- *Immune Cells.* Immune cells from blood and peritoneal washings will be collected at baseline (prior to seroconversion dose on Cycle 1 Day 1), prior to treatment on Cycle 2 Day 1, prior to treatment on Cycle 4 Day 1, and at disease progression or off treatment, and 30-day off treatment follow-up.
- *Plasma.* Collected at baseline (prior to seroconversion dose on Cycle 1 Day 1), prior to treatment on Cycle 1 Day 22, prior to treatment on Cycle 2 Day 1, prior to treatment on Cycle

3 Day 1, prior to treatment on Cycle 4 Day 1, and at disease progression or off treatment, and 30-day off treatment follow-up.

- *Pharmacogenomics.* Subjects will have whole blood collected at baseline.

TABLE OF CONTENTS

PROTOCOL VERSIONS	2
SPONSOR CONTACT INFORMATION	3
PROTOCOL SYNOPSIS	4
TABLE OF CONTENTS	8
LIST OF ABBREVIATIONS	10
1.0 INTRODUCTION	11
1.1 Background	11
1.2 Study Drug	12

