3.0 STUDY DESIGN

3.1 Study Description

This is a non-randomized, open-label Phase I trial in patients with Stage IV peritoneal surface dissemination from gastrointestinal, fallopian tube, ovarian, or primary peritoneal tumors enrolled at Duke Cancer Institute and select external collaborating institutions. All subjects will complete an extensive medical history, baseline physical examination and clinical assessment to ensure subject eligibility requirements (see Eligibility Criteria for details) within 4 weeks of starting study drug. All eligible patients must have a peritoneal catheter placed prior to the initiation of therapy. All patients will receive an initial seroconversion dose of talimogene laherparepvec 4×10^6 PFU on Cycle 1 Day 1 to enable seroconversion as described in the currently approved treatment protocol for the treatment of cutaneous melanoma. Three weeks (+3 days) after the initial seroconversion dose, patients will receive talimogene laherparepvec at the dose level for the cohort for which they are enrolled every 2 weeks (± 3 days) for up to 4 doses. The length of the first cycle is 5 weeks and subsequent cycles are 2 weeks in duration.

- Enrolled subjects are defined as subjects who give informed consent.
- Screen failures are defined as subjects who give informed consent and do not meet eligibility criteria.
- Accrued subjects are defined as subjects who give informed consent and meet eligibility criteria.
 - Withdrawal: Subject accrued but later withdrawn from the study, either before or after receiving a study drug.
 - Evaluable: In the Dose Escalation Cohort, subjects who are accrued, received study treatment, and completed the first cycle of safety assessments or have dose limiting toxicity (DLT) which is study treatment related that precludes completing the full cycle of assessments will be considered evaluable for DLT. All subjects (in Dose Escalation and Dose Expansion) who are accrued and receive any study treatment will be considered evaluable for toxicity. All subjects in Dose Escalation and Dose Expansion who are accrued and receive any study treatment will be considered evaluable for efficacy.
 - Non-evaluable: In the Dose Escalation Cohort, subjects who accrued but did not complete the first cycle of safety assessments due to reasons other than study treatment-

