Interestingly, it was recently shown that immunity against peritoneal tumors is somewhat unique with regard to mechanisms of protection[16]. The peritoneal cavity harbors resident leukocyte types that are phenotypically and functionally distinct from their counterparts in other anatomic locations. These include B-1b cells[17], peritoneal NK cells[18], and peritoneal macrophages[19]. The functions of these cells in immunity against tumors of the peritoneal cavity is largely unexplored. This exploratory aim is innovative in that we will seek to elucidate changes in the peritoneal tumor immune microenvironment after treatment with different doses of talimogene laherparepvec. This information will facilitate the rational design of combination therapies to target anti- and pro-tumor immune effectors that are relevant to PSD of gastrointestinal, fallopian tube, ovarian, and primary peritoneal cancers.

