8.5 Viral Load

Plasma and urine samples will be collected at the following time points: baseline (prior to seroconversion dose on C1D1), C1D8, C1D15, prior to treatment on C1D22, C1D29, prior to treatment on C2D1, prior

to treatment on C3D1, prior to treatment on C4D1, and at 30-day off treatment follow up visit. Peritoneal fluid will be collected at baseline (prior to seroconversion dose on C1D1), prior to treatment on C2D1, prior to treatment on C4D1, and 30-day off treatment follow-up. If the subject comes off treatment mid cycle, take an additional plasma and peritoneal sample at the time of disease progression or off treatment.

Plasma, urine and peritoneal fluid will be collected, frozen and stored at the site (at -80) until such time as deemed appropriate for analysis. When ready for viral load analysis, plasma, urine and peritoneal fluid samples will be shipped to [name] lab at LSU. A quantitative primer will be used to detect HSV-1 DNA in plasma, urine, and peritoneal fluid samples via polymerase chain reaction (PCR).

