9.1.4 Exploratory Endpoints

In addition to defining the MTD, the study will provide useful preliminary data concerning efficacy. Methods of assessing response will be specific to each individual patient as described in Section 5.6. In the subset of patients with radiographically measurable disease RECIST 1.1 criteria will be used.

Patients in the per protocol population will be classified as responder or non-responder and the proportion of patients exhibiting response at trial closure by any criteria will be estimated by the 90% confidence interval. Patients who experience a radiographic/tumor marker CR will undergo confirmatory laparoscopy.

Time to progression measured from study entry to documented progression of disease will be estimated by the method of Kaplan-Meier in the intent-to-treat population. Patients who withdraw from the trial prior to disease progression, are either lost to follow-up, die or begin alternative treatments prior to progression, will be censored at the date considered to be lost to follow-up, date of death, or the first day of alternative therapy.

For all efficacy endpoints, analyses will be performed overall and in the patients treated at the MTD. These analyses are primarily exploratory since the data will be from only a limited number of patients available for the study.

As a first approach to addressing our exploratory aim of evaluating changes in peritoneal cavity leukocyte populations after the treatment of peritoneal surface dissemination of gastrointestinal, fallopian tube, ovarian, and primary peritoneal cancers with talimogene laherparepvec, we will perform multi-color flow cytometry analysis on peritoneal lavage fluid from patients at baseline (prior to seroconversion dose on C1D1), prior to treatment on C2D1, and on C4D1. If the subject comes off treatment mid cycle, there will be an additional plasma sample at the time of disease progression or off treatment. Immune cells will be stained with fluorescent antibodies specific for markers of major leukocyte subsets as commonly performed by the [name] Lab.

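### Section 9.1.3 limits its 90% intervals for viral load, cytokines and immune markers to subjects treated at the MTD and plans no by-dose summary, although every subject is sampled and all share the same first dose

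*Combined protocol and SAP*

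**What the plan says.** All references are to the combined protocol and SAP.

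- **Analysis set.** Section 9.1.3 states that 90% interval "estimates of mean changes in viral load, cytokine levels, and immune markers from baseline will be constructed in the intent-to-treat population (n=12" subjects). Section 9.1 says: "The intent to treat population is defined as all subjects who receive treatment with talimogene laherparepvec at the MTD". The precision statement in 9.1.3 uses the same set: "With 12 patients studied in the intent-to-treat population the 90% upper confidence bound (1-sided) for change in viral load is at most 0.185".
- **Who is sampled.** The synopsis (Correlative Studies) describes "blood and tumor tissue specimen collections and specified time points from all subjects". Section 8.2 likewise collects immune cells from each subject.
- **Common first dose.** Section 3.1: "All patients will receive an initial seroconversion dose of talimogene laherparepvec", at 4×10^6 PFU. The first cohort-level dose follows three weeks later, on C1D22.
- **Early samples.** Section 8.5: "Plasma and urine samples will be collected at the following time points: baseline (prior to seroconversion dose on C1D1), C1D8, C1D15", then pre-dose C1D22 and later visits. Section 8.3 adds plasma at pre-dose C1D22, with aliquots of all plasma samples kept for cytokine analysis.
- **Aims.** Viral load in plasma, urine and peritoneal fluid is the only secondary objective (2.2), and it is not limited to the MTD. Section 8.0 describes the exploratory aim as "changes in the peritoneal tumor immune microenvironment after treatment with different doses of talimogene laherparepvec".
- **Breakdowns planned elsewhere.** Adverse events are summarised overall and by dose level (9.1.2). Efficacy endpoints are analysed overall and at the MTD (9.1.4). The leukocyte paragraph of 9.1.4 says "we will perform multi-color flow cytometry analysis on peritoneal lavage fluid from patients at baseline" and at later visits. It does not restrict this to the MTD and gives no dose breakdown.

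**The concern.** The plan names a narrower analysis set than its secondary objective and its sampling call for. Two things are lost.

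First, any change in viral load or immune markers with dose has no planned description, although the samples are taken and section 8.0 states the aim. A dose-escalation study is the natural place to show it: level 3, if it opens, is 4×10^8 / 4×10^6 = 100 times level 1.

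Second, some samples are taken before assigned level can have influenced exposure. Leaving non-MTD subjects out of those intervals costs precision on the secondary objective for no exposure-related reason.

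**Working it through.** **1. The plan's own figures.** The maximum normal-approximation margin for a proportion (p = 0.5) is z × sqrt(0.25/n). With n = 12:
- one-sided 90%: 1.2816 × sqrt(0.25/12) = 0.185, as stated for viral load;
- two-sided 90%: 1.6449 × sqrt(0.25/12) = 0.237, as stated for cytokines.

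Both reproduce, so the precision statement does rest on 12 subjects. Twelve is 6 escalation subjects at the MTD (3.2) plus 6 expansion subjects (3.3). Section 3.2 says up to 6, so 3 + 6 = 9 is possible if level 3 becomes the MTD after only 3 subjects.

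**2. Subjects outside the intervals.** Table 3.1 gives 3-6 subjects at each other opened level.

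| MTD | At MTD | Outside | Total | Share outside |
|---|---|---|---|---|
| Level 2 or 3 | 12 | 6-12 | 18-24 | 6/18 = 33% to 12/24 = 50% |
| Level 3 after 3 subjects | 9 | 6-12 | 15-21 | 6/15 = 40% to 12/21 = 57% |
| Level 1, by assigned level | 12 | 3-6 | 15-18 | 3/15 = 20% to 6/18 = 33% |

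If level 1 is the MTD, its dose equals the seroconversion dose. Read literally, 9.1 then includes every treated subject and nobody is outside. These counts follow Table 3.1 and the synopsis maximum of 24. Section 9.1 says up to 30, which the documents do not reconcile.

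**3. Which samples precede any cohort-level dose.**
- Plasma and urine viral load: C1D8, C1D15, pre-dose C1D22.
- Plasma cytokines: pre-dose C1D22.
- Peritoneal fluid and immune cells: none. Their first sample after baseline is at C2D1, after the C1D22 cohort dose.

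**4. Precision of a mean log change.** The 90% half-width in SD units is t(0.95, n−1)/sqrt(n):
- n = 12: 1.796/3.464 = 0.52
- n = 18: 1.740/4.243 = 0.41
- n = 24: 1.714/4.899 = 0.35

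Pooling at the common-dose times would therefore narrow the interval by 1 − 0.410/0.518 = 21% to 1 − 0.350/0.518 = 32%. For 9 subjects at the MTD the half-width is 1.860/3 = 0.62 SD.

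A single dose level gives 2.920/1.732 = 1.69 SD at n = 3 and 2.015/2.449 = 0.82 SD at n = 6.

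**5. The same margin for a proportion (one-sided 90%, p = 0.5).** It is 0.185 at n = 12, 1.2816 × sqrt(0.25/18) = 0.151 at n = 18, and 1.2816 × sqrt(0.25/24) = 0.131 at n = 24.

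**The case against.** **Overall summaries may already be planned.** Section 9.1.1 applies the analyses to the intent-to-treat, per protocol and safety populations and lists descriptive statistics for quantitative variables. The sentence in 9.1.3 on the proportion with a 2-log change names no population, and the leukocyte paragraph of 9.1.4 is not limited to the MTD. A reader might infer that data from non-MTD subjects will go unanalysed. The documents do not support that. What stands is narrower: none of these places gives a dose breakdown, pooling after C1D22 mixes doses, and the stated intervals remain in the MTD set.

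**Groups of 3-6 are too small.** This is true for inference (step 4). Section 9.1.1 already makes all analyses descriptive, and adverse events are tabulated by level on the same groups.

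**The precision gain may be smaller than it looks.** Section 1.2.1.2 reports that after intralesional injection viral DNA was found sporadically, in blood from 33% of subjects and urine from 22%, between 1 hour and 1 week. Samples were negative by 2 weeks where later ones were available. The route differs, so this is indirect. If intraperitoneal dosing behaves similarly, many C1D15 and C1D22 values will be undetectable and a mean log change will describe them poorly. This stands, and it is why the proportion with detectable virus belongs in the plan.

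**The 0.185 figure.** A reader might take it as the precision at the early visits. It is a worst-case margin for a proportion at n = 12 and is tied to no visit, so step 5 shows only how that general margin scales with n.

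**The text on interval scope is damaged.** The sentence containing n=12 lacks its closing bracket, and the confidence-interval line in 9.1.1 is garbled. The next paragraph of 9.1.3 repeats 12 subjects in the intent-to-treat population, which supports the reading used here.

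**Conclusion.** The point holds. The 90% intervals for mean change in viral load, cytokines and immune markers are confined to the MTD set, and no by-dose summary of these endpoints is planned. With level 2 or 3 as the MTD, 6-12 of 18-24 subjects are outside the intervals (12 at the MTD), or 6-12 of 15-21 if only 9 are treated there. At the common-dose times the half-width for a mean log change could fall from 0.52 SD to 0.41 or 0.35 SD. That assumes 12 at the MTD, a usable sample from every treated subject, and values to which a mean log change is suited.

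Two stronger inferences fail. Pooling is not justified for every sample: from C1D29 onward subjects have received cohort-level doses. Nor is the primary objective or any escalation decision affected, since those rest on DLTs and on adverse-event summaries that already cover all dose levels. The change should be made, but the trial's main purpose does not depend on it.

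**What to change.** In 9.1.3, state:

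> Viral load, cytokines and immune markers will be summarised descriptively by assigned dose level as well as overall in all treated subjects. For samples taken after the seroconversion dose and before the first cohort-level dose (plasma and urine viral load at C1D8, C1D15 and pre-dose C1D22; plasma cytokines at pre-dose C1D22), 90% intervals, and the proportion with detectable virus for viral load, will be given for all treated subjects pooled. For later samples, 90% intervals will be given for the MTD set.

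In 9.1, define the MTD set once, as subjects assigned to the MTD level, and use that definition throughout. This also removes the ambiguity that arises if level 1, whose dose equals the seroconversion dose, is the MTD.

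In the leukocyte paragraph of 9.1.4, add: overall and by assigned dose level.

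The cost is a few sentences and some extra tables, with no new samples, visits or subjects. The downside is that by-level results at 3-6 subjects are imprecise and must be labelled descriptive.
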